In a recent observational study in LTC facilities ¹² we reported i) a diabetes prevalence of 32.5% with most patients treated with oral antidiabetic drugs (OADs) alone or in combination with sliding scale regular insulin, ii) high frequency (44%) of hypoglycemic events, and iii) residents with hypoglycemia have a longer length of stay, emergency room or hospital transfers, and higher mortality compared to those without hypoglycemia (see preliminary results). In a pilot study in LTC patients with diabetes, we randomized 100 patients with diabetes to receive low-dose basal (glargine) insulin and rapid-acting insulin before meals or to continue OADs (metformin and/or sulfonylurea) plus regular insulin before meals for BG > 200 mg/dl. We observed similar improvement in HbA1c at 3 and 6 months and in the frequency of hypoglycemia (basal 28% vs. control 31%; please see preliminary results). The results of our preliminary studies indicate the need for safe and effective protocols to achieve glucose control with a low rate of hypoglycemia. We propose two strategies that have been shown to improve glucose control with low rates of hypoglycemia in the hospital, which could be easily implemented in LTC facilities ^{13,14}. The 'basal plus' approach with a daily dose of glargine plus correction doses of rapid-acting insulin was shown to be as effective as basal bolus regimen in improving glucose control in general medicine and surgery patients with type 2 diabetes (T2D) ¹³. The sitagliptin inpatient trial ¹⁴ reported that treatment with DPP4 inhibitor alone or in combination with insulin glargine results in similar glucose control compared to a basal bolus regimen in inpatients with T2D. No clinical trials have determined the safety and efficacy of basal insulin (standard of care) and DPP4 inhibitors in LTC facilities. *Accordingly, we propose a prospective randomized controlled trial comparing treatment with a DPP4 inhibitor (linagliptin) to a basal plus (glargine) regimen (\pm metformin for both treatments) in LTC residents with T2D.*

Specific Aim and Hypothesis:

Aim 1. To determine whether glycemic control, as measured by change in mean BG, HbA1c and frequency of hypoglycemia, is different between treatment with linagliptin (Tradjenta®) and basal insulin in LTC residents with T2D. Patients with poorly controlled diabetes (HbA1c >7.5%) will be randomized to a 6-month intervention with linagliptin or glargine

insulin (\pm metformin for both treatments).

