Diabetes and Clinical Outcome in Long-term Care Residents ¹². This observational study analyzed the quality of diabetes care, glycemic control, and clinical outcome in 1,409 subjects admitted to 3 community LTC facilities in Atlanta. The prevalence of diabetes was 34.2%. On admission, patients with diabetes were either on no pharmacological agents (10%) or were treated with, sliding scale regular insulin (SSI, 25%), OADs (5%), insulin (34%), or with combination of OADs and insulin (26%). Patients with diabetes had higher number of complications ($p<0.001$) and required more emergency room and hospital transfers ($p=0.013$). A Cox proportional hazards model revealed that a history of diabetes is associated with a higher risk of mortality (HR: 1.44, $p=0.027$). A total of 42% of patients had ≥ 1 episode of BG <70 mg/dl and 7% had a BG <40 mg/dl. Hypoglycemia was reported in 45% on OADs (mostly sulfonylurea plus SSI), 53% on glargine, 67% on NPH or premixed insulin, 20% patients on SSI alone. Patients with hypoglycemia had a longer length of stay ($p<0.001$), higher emergency room or hospital transfers (44% vs. 30%; $p=0.004$) and higher mortality (18% vs. 10%, $p=0.015$). These results indicate that diabetes is common in LTC and is associated with higher resource utilization and complications, and that hypoglycemia is associated with increased rates of emergency room care and hospitalization, length of stay, and mortality ¹².

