A total of 150 male or female LTC residents with type 2 diabetes with an fasting or random BG >/= 180 mg/dL and/or an A1c > 7.5% while receiving treatment with diet (no pharmacological therapy), OADs (metformin, secretagogues, thiazolidinediones), low dose insulin of 0.1U/kg/day or sliding scale regular insulin will be randomized to receive linagliptin or glargine insulin therapy.

This study will be performed at Crestview, a community LTC institution affiliated with Grady Health System; Budd Terrace on the Wesley Woods campus of Emory University; and the Community Living Center at the Atlanta VA Medical Center, Atlanta.

IV.c. Primary and Secondary Research Outcomes:

[figure not shown]
The primary endpoint of the study is change in mean BG over a 6-month treatment period between treatment with basal plus insulin regimen and aDPP4 inhibitor in LTC residents with poorly controlled diabetes.

Secondary outcomes include differences between treatment groups in any of the following measures:

1. Percentage of HbA1c ≤ 7.5% at 3 or 6 month independent of the occurrence of hypoglycemia.
2. Occurrence rate and total number of hypoglycemic events (<70 mg/dl) and severe hypoglycemia (< 40 mg/dl).
3. Total daily dose of insulin, metformin and linagliptin.
4. Change in hemoglobin A1c over a 6-month treatment period
5. Changes in cognitive function assessed by mini-mental examination.
6. Prevalence of acute complications (urinary tract infections, pneumonia), bedsores, diabetic foot infection.
7. Need for emergency room visits or hospitalizations during the study period.
8. Cardiac complications are defined as myocardial infarction, cardiac arrhythmia and heart failure.
9. Acute renal failure defined as a clinical diagnosis of acute renal failure with documented new-onset abnormal renal function (increment > 0.5 mg/dL from baseline).

10. Hospital mortality. Mortality is defined as death occurring during admission.

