- **Insulin adjustment.** The total daily insulin dose will be adjusted as follow:
 - Fasting and pre-meal BG between <180 mg/dl without hypoglycemia the previous day: no change
 - Mean fasting and pre-meal BG between 181-280 mg/dl without hypoglycemia: increase glargine dose by 10% every 3 days
 - Mean fasting and pre-meal BG >281 mg/dl without hypoglycemia: increase glargine dose by 20% every 3 days
 - Mean fasting and pre-meal BG between <100 mg/dl: decrease glargine dose by 10% every day
 - If a patient develops hypoglycemia (<70 mg/dL), decrease glargine dose by 20%.
 - If a patient develops hypoglycemia (<40 mg/dL), decrease glargine dose by 30-40%.
- **Blood glucose monitoring.** Blood glucose will be measured before each meal (or every 6 hours if a patient is not eating) using a glucose meter. In addition, blood glucose will be measured at any time if a patient experiences symptoms of hypoglycemia or if requested by the treating physician.

IV.f. Investigational drugs.

1. Linagliptin (Tradjenta®) 5 mg tablets for oral administration. Linagliptin is not a formulary drug at Grady Health System and VAMC and will be provided by Boehringer Ingelheim Pharmaceuticals, Inc (see letter of support, page 76)
2. Glargine insulin: U-100/mL, provided in 10 mL vials. Glargine (Lantus®) is available in all institutions.

IV.g. Withdrawal Criteria

1. The subject may withdraw at any time during the study by primary care provider or research team.
2. The subject may be withdrawn at the investigator's discretion due to a safety concern or if judged non-compliant with trial procedures or for contravention to the inclusion and/or exclusion criteria.
3. Subject diagnosed with acute pancreatitis by clinical and/or radiographic criteria.
4. Patients with severe hyperglycemia defined as 3 consecutive BG levels > 280 mg/dl or 2 consecutive days with an average BG > 280 mg/dL will be considered as failure and discontinued from the study. Patients receiving linagliptin therapy will be switched to basal plus insulin and those on basal insulin will be switched to basal bolus insulin regimen.

IV.h. Subject Replacement

There will be no replacement of subjects in this trial.

IV.i. During follow up we will collect the following information

1. Glycemic control:
 - a. Mean daily fasting and premeal blood glucose levels.
 - b. HbA1c at baseline, 3 and 6 months of discharge
 - c. Number of hypoglycemic events
2. Diabetes treatment:

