VIII.a. Sample Size and Power Calculations: This study is randomized, open-label controlled trial. The primary endpoint in this study is glycemic control measured change determined by mean daily blood glucose concentrations and in HbA1c at 3 and 6 months of intervention. The median stay at all facilities was 48.9 ± 50 days, therefore the study did not have power to determine a statistical change in glycated hemoglobin at 6 months. The primary endpoint of the study was modified to evaluate the difference between treatment with basal insulin and linagliptin on glycemic control determined by mean daily blood glucose concentrations during LTC stay, as previously reported (62). Main secondary endpoints included differences in the frequency of hypoglycemia, fasting glucose, HbA1c at 3 and 6 months of intervention, complications, emergency room visits and hospitalizations. We made the comparisons using non-parametric Wilcoxon tests for continuous variables and χ^2 tests (or Fisher's exact test) for discrete variables. We summarize demographics, baseline clinical characteristics, and clinical outcomes by the two treatment groups. Data is presented as mean \pm standard deviation for continuous variables and present count (percentage) for categorical variables. Glycemic variability was calculated by standard deviation (SD) of glucose values during entire study and by the mean daily delta (Δ) daily range of blood glucose (daily max – daily min- mum)(20, 24).The data were presented as mean (SD) for continuous variables and count (percentage) for discrete variables unless specified otherwise. We performed statistical analyses with SAS version 9.3.

VIII.b. Analysis of Primary Endpoint:

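### HbA1c is timed from discharge in the collection schedule (IV.i) but from the start of intervention in the endpoint definitions (IV.c, VIII.a), and the plan does not reconcile the two

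*Combined protocol and SAP*

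**What the plan says.** The collection list in IV.i sets HbA1c at "HbA1c at baseline, 3 and 6 months of discharge".

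The endpoint sections count from treatment. VIII.a lists among the main secondary endpoints "fasting glucose, HbA1c at 3 and 6 months of intervention". Secondary outcome 4 in IV.c is "Change in hemoglobin A1c over a 6-month treatment period". Secondary outcome 1 in IV.c, "Percentage of HbA1c ≤ 7.5% at 3 or 6 month independent of the occurrence of hypoglycemia", gives no starting point. Aim 1 in section I says that patients "will be randomized to a 6-month intervention with linagliptin or glargine".

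VIII.a also reports that "The median stay at all facilities was 48.9 ± 50 days" and continues: "therefore the study did not have power to determine a statistical change in glycated hemoglobin at 6 months". It then limits the primary endpoint to mean daily glucose during the stay, but keeps HbA1c at both 3 and 6 months. Its stated method for continuous variables is the Wilcoxon test, without adjustment for baseline. No section says whether HbA1c is drawn after discharge, whether study treatment continues then, or how missing HbA1c values are handled.

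**The concern.** IV.i is the instruction that a study coordinator follows. Read literally, it produces values taken a fixed time after each resident has left, at a different time since randomization for each person. VIII.a and IV.c define a value at a fixed time on treatment. These are different quantities, and the first cannot stand in for the second.

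The second issue appears once the anchor is corrected. With stays near seven weeks, most residents may have left before the 3-month sample. If HbA1c is not collected from those who leave, the arms are compared among people selected after randomization, and the comparison loses the protection of randomization. A non-significant test in so small a remainder could be taken as support for the Aim 1 hypothesis of similar improvement in glucose control, when it would show little either way.

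**Working it through.** **1. The anchors side by side.**

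| Place | What is timed | Counted from |
|---|---|---|
| IV.i, item 1b | HbA1c collection, 3 and 6 months | discharge |
| VIII.a | HbA1c endpoint, 3 and 6 months | intervention |
| IV.c, outcome 4 | HbA1c change, 6 months | treatment period |
| IV.c, outcome 1 | HbA1c at or below 7.5%, 3 or 6 months | not stated |

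IV.i is the only place that counts from discharge.

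**2. Effect on timing.** Inputs: stay 48.9 days (VIII.a); 3 and 6 months taken as 90 and 180 days; stay counted from randomization (assumption).

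- From intervention: days 90 and 180.
- From discharge: 48.9 + 90 = 138.9 and 48.9 + 180 = 228.9, so about days 139 and 229.
- The shift is 48.9 / 7, about 7 weeks, for that resident. Because the sampling day is own stay plus a constant, its SD across residents equals the SD of stay, about 50 days if that is what the ± figure means.

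**3. Share still resident at 3 and 6 months.** The stay is an observed summary, so there is no calculation in the plan to reproduce. The figure is labelled a median but carries a ± term, so both readings are tried with SD = 50.

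*48.9 as the mean, lognormal:* σ² = ln(1 + (50/48.9)²) = ln(2.0455) = 0.716, σ = 0.846; median = 48.9 / exp(0.358) = 34.2.
- P(stay > 90) = 1 − Φ(ln(90/34.2)/0.846) = 1 − Φ(1.144) = 0.126
- P(stay > 180) = 1 − Φ(1.963) = 0.025

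*48.9 as the mean, gamma:* shape (48.9/50)² = 0.956, scale 2500/48.9 = 51.1, giving 0.161 and 0.027.

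*48.9 as the median, lognormal:* solve 48.9·exp(σ²/2)·√(exp(σ²) − 1) = 50. The mean is then 62.6 and σ = 0.703.
- P(stay > 90) = 1 − Φ(0.610/0.703) = 0.193
- P(stay > 180) = 1 − Φ(1.303/0.703) = 0.032

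*48.9 as the median, gamma:* mean 61.7, shape (61.7/50)² = 1.52, scale 2500/61.7 = 40.5, giving 0.223 and 0.032.

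With calendar months (91.3 and 182.6 days) the four results are 0.123, 0.156, 0.187 and 0.217 at 3 months, and 0.024, 0.026, 0.030 and 0.030 at 6 months. The range over all of these is about **12-22% at 3 months and 2-3% at 6 months**.

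*Counts, both arms together:* of the 140 in VIII.b, 140 × 0.123 = 17 to 140 × 0.223 = 31 at 3 months, and 140 × 0.024 = 3.4 to 140 × 0.032 = 4.5 at 6 months. Of the 150 in IV.b, 18 to 33 and 3.6 to 4.8.

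**4. What does not depend on the assumed shape.** If 48.9 is a median, at most half remain at 90 days. If it is a mean with SD 50, the one-sided Chebyshev (Cantelli) bound allows up to 2500/(2500 + 41.1²) = 0.597 at 90 days and 2500/(2500 + 131.1²) = 0.127 at 180 days. The narrower range in step 3 therefore rests on the distributions chosen.

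**The case against.** The strongest reply is that IV.i contains a wording slip. Every other dated statement about HbA1c or the glycemic endpoint counts from treatment, so the intended schedule is clear. The sponsor has also seen the short stay, conceded the lack of power at 6 months, and moved the primary endpoint accordingly. HbA1c carries no confirmatory claim.

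Most of this stands. It lowers the severity, but the collection instruction remains wrong, and the concession covers only power at 6 months. It covers neither the 3-month value nor selection.

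Four stronger readings are tempting, and the documents do not support them.

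- *HbA1c exists only for residents still in the facility.* No section says that treatment or collection stops at discharge. Aim 2 compares events over the six months of intervention, and IV.i itself contemplates data after discharge. The other reading is plausible, because VIII.a gives stay as the reason for low power and cuts the primary window to the stay, and XII has glargine dispensed by the inpatient pharmacy. It is still an inference.
- *Treatment arm changes length of stay through hypoglycemia.* Section III reports that "Patients with hypoglycemia had a longer length of stay", and sections IX and X expect more hypoglycemia on basal insulin. The reported association is observational and may run in reverse, since a longer stay gives more time to record a low glucose. Differential selection is possible, not shown.
- *As many as 28% and 8% could remain.* Those shares come from an exponential stay with median 48.9: 0.5^(90/48.9) = 0.279 and 0.5^(180/48.9) = 0.078. Its SD is 48.9/ln 2 = 70.5 days, not 50.
- *HbA1c must leave the tested endpoints, or a mixed model would solve the problem.* Removal is a debatable trade-off that also touches Aim 1 and secondary outcomes 1 and 4. A mixed model would draw on the same few scheduled values and would assume that missingness is ignorable.

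**Conclusion.** The conflict between IV.i and the endpoint sections is certain from the current text. For a 48.9-day stay it moves the samples by about seven weeks, and a site following IV.i would collect values that are not the defined endpoint. Whether any site has done so is unknown.

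The 12-22% and 2-3% figures are conditional. They require that treatment or collection ends at discharge, that stay has SD 50 with 48.9 as its mean or median, and that stay is roughly lognormal or gamma. VIII.a does not say whether stay runs from admission or randomization, or whether it describes participants or all residents; both affect the counts. Under these assumptions the HbA1c comparison would rest on about 17 to 31 of 140 residents at 3 months and 3 to 5 at 6 months, selected after randomization. Severity is minor to moderate, because the primary endpoint does not depend on HbA1c timing.

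**What to change.** 1. Reword IV.i so that HbA1c is timed from randomization, and use that anchor in IV.c (including outcome 1) and VIII.a.
2. State whether HbA1c is still collected after discharge, and whether study treatment continues then. If samples have already been drawn, record each one's date relative to randomization and to discharge, so that values can be assigned to the correct time.
3. At baseline, 3 and 6 months, report the number measured per arm, with the baseline HbA1c of those measured.
4. Replace the unadjusted Wilcoxon comparison of HbA1c with a baseline-adjusted one, such as analysis of covariance. The baseline value is already collected. Adjustment corrects for baseline HbA1c only and does not undo selection on other factors.
5. Keep HbA1c as a secondary endpoint, labelled exploratory, and state in advance that a null result in the residents measured will not be read as evidence of similar control.

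The cost is wording in three sections, a few table columns and one model. The anchor correction and the adjustment change neither the sample size nor the primary analysis. If the sponsor chooses to collect HbA1c after discharge, the added cost is tracing and sampling residents who have left.

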IV.d. Plan. This study will include male or female subjects admitted to LTC affiliated with Grady Health System, Emory University Hospital, and VAMC in Atlanta, Georgia. Due to the design of this study (i.e. enrollment of subjects admitted for LTC), there will be no run-in period. All residents with a known history of diabetes and an HbA1c >7.5% despite treatment with diet (no pharmacological therapy), stable dose of OADs (metformin, secretagogues, thiazolidinediones), or sliding scale insulin therapy will be considered as potential candidates in this study. The consent form will be presented and discussed to primary care team, and participants and/or relatives prior to participation in the study.

- Patients receiving no pharmacological agents will be randomized to receive once daily linagliptin or glargine insulin as monotherapy.
- Patients receiving OADs will discontinue these agents at enrollment with the exception of metformin (unless contraindication). Patients will continue therapy with metformin at the same dosage and will start combination therapy with linagliptin or glargine insulin (add-on therapy).
- Patients who are not candidate to metformin therapy (i.e., reduced kidney function or GI intolerance) will be treated with once daily linagliptin or glargine insulin as monotherapy.
- For safety reason, patients in both groups will receive supplemental (correction) doses of rapid-acting insulin (lispro or aspart) before meals for BG > 200 mg/dl.
- The goal of therapy is to maintain fasting and pre-meal blood glucose <180 mg/dL and an A1C <7.5% while avoiding hypoglycemia.

IV.e. Study Groups:

Group 1. Basal Plus regimen with glargine once daily \pm metformin, n= 75

Group 2. Linagliptin once daily \pm metformin, n=75

GROUP 1. Linagliptin Group.

- Discontinue oral antidiabetic drugs (except metformin if no contraindication), insulin and non-insulin injected antidiabetic medication on admission.
- Start linagliptin 5 mg once daily
- Start accucheks with meals and at night. Can reduce to twice a day when appropriate.

GROUP 2. Glargine Insulin Group

- Discontinue oral antidiabetic drugs (except metformin if no contraindication), insulin and non-insulin injected antidiabetic medication on admission.
- Start accucheks with meals and at night. Can be reduce to twice a day when appropriate.
- Starting total daily insulin dose: 0.1 units per kg once daily at the same time of the day.

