Hyperglycemia: supplemental insulin will be given before meals to cover for BG >200 mg/dL. Patients with persistent hyperglycemia defined as 3 consecutive BG levels > 280 mg/dL or 2 consecutive daily average >15.5 mmol/L (280 mg/dL) will be considered as failure and will be discontinued from the study. Patients receiving linagliptin will be switched to basal and those on basal will be switched to basal bolus regimen.

Acute renal failure: patients with GFR <45 ml/min will not be treated with metformin.

XI. Data handling and record keeping: Data collection records with personal identifiers will be stored in locked file cabinets. No blood samples will be stored in this study. Access to research will be limited to clinical investigators, research coordinators, and the IRB at Emory University.

XII. Storage and Drug Accountability of Study Medication(s). Linagliptin will be stored and dispensed by the research pharmacy at each institution. Glargine insulin is standard of care and is available at the three participating institutions and will be dispensed by general inpatient pharmacy.

XIII. Randomization and Blinding. This is an open label randomized controlled trial. Patients will be randomized consecutively using a computer generated randomization table provided by [name] at the Emory School of Public Health. The randomization table will be mailed to the research pharmacist at each institution who will be in charge of the randomization and group assignment.

XIV. Informed Consent. Informed consent will be obtained before any trial related procedures including screening procedures. The consent form will follow the IRB guidelines of Emory University. A signed copy of the consent will be provided to the participant and a copy of the consent will be placed in the study office.

XV. Inclusion of women: We anticipate that ~50% of the study subjects will be female.

XVI. Inclusion of minorities: Patients will not be excluded based on race or ethnic origin. We anticipate that half of patients will be African Americans, 10% Hispanics, and the rest Caucasians.

XVII. Inclusion of children: No patients under the age of 18 will be recruited in this study.

XVIII. Financial Conflict of Interests. None of the investigators in this study have any outside activities that may represent a conflict of interest.

XIV. Data Safety Monitoring Plan.

A Data Safety Monitoring Board or Safety Officer has been designated for this study.

[name]
Department of Medicine/Endocrinology

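### The mean daily glucose range in VIII.a depends on how many readings a day holds, and the plan lets that number vary without fixing which readings count

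*Combined protocol and SAP*

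**What the plan says.** Section VIII.a defines glycemic variability twice in one sentence. The first measure is a whole-study SD: "Glycemic variability was calculated by standard deviation (SD) of glucose values during entire study". The second is the mean over days of the "daily range of blood glucose (daily max" minus the daily minimum. The section compares continuous variables with Wilcoxon tests.

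The number of readings in a day is not fixed:

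- **IV.e, linagliptin list:** "Start accucheks with meals and at night. Can reduce to twice a day when appropriate". The glargine list starts the same way and adds "Can be reduce to twice a day when appropriate". Neither gives a criterion for the cut or says which two checks remain.
- **IV.e, blood glucose monitoring item** (printed after the glargine items but worded for patients generally): "Blood glucose will be measured before each meal (or every 6 hours if a patient is not eating) using a glucose meter". It mentions no reduction.
- **Same item, unscheduled readings:** "blood glucose will be measured at any time if a patient experiences symptoms of hypoglycemia or if requested by the treating physician".
- **VII.b:** after a value below 70 mg/dL, finger-stick checks are repeated every 15 minutes until glucose exceeds 100 mg/dL.

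No section sets a minimum number of readings per day, names the check times that enter the daily range, or says whether unscheduled readings count. Section XIII states: "This is an open label randomized controlled trial".

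**The concern.** A range is built from the two most extreme values, so it tends to grow with the number of values even when the underlying variability is the same. Taken literally, the rule gives the same resident a smaller score on a two-check day than on a four-check day. A day with one reading scores zero.

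This matters between arms only if testing frequency differs between arms. Three features of the protocol make that plausible:

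- Staff know the assignment, so a decision to cut checks can depend on it.
- Only glargine has a dose rule driven by fasting and pre-meal readings, for example "Mean fasting and pre-meal BG between 181-280 mg/dl without hypoglycemia: increase glargine dose by 10% every 3 days". That is a reason to keep testing that arm.
- Section IX expects hypoglycemia in about 20% of residents on basal insulin (section X says about 12%) against under 5% on linagliptin. This implies more symptom checks and 15-minute rechecks on glargine, each of which can widen that day's range and none of which can narrow it.

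All three would lower the daily range on linagliptin relative to glargine. A Wilcoxon comparison could then report steadier glucose on linagliptin that reflects testing frequency alone.

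**Working it through.** The documents give no figure for variability and no within-day SD, so there is nothing of theirs to reproduce. The within-day SD cancels in the ratios of step 1.

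**1. Expected range of k independent normal readings.** E[range] = SD × d2(k), where d2(k) = ∫[1 − F(x)^k − (1 − F(x))^k] dx and F is the standard normal distribution function.

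| Readings per day | d2(k) |
|---|---|
| 4 (meals and night) | 2.059 |
| 3 (before each meal) | 1.693 |
| 2 (after the cut) | 1.128 |

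- Four to two: 1 − 1.128/2.059 = 45.2% lower.
- Four to three: 1 − 1.693/2.059 = 17.8% lower.
- Three to two: 1 − 1.128/1.693 = 33.3% lower.

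With an assumed within-day SD of 35 mg/dl, four checks give 2.059 × 35 = 72.1 mg/dl and two give 1.128 × 35 = 39.5 mg/dl.

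**2. Sensitivity of the 45% (all inputs assumed).** The direction is certain, because the range of a subset cannot exceed the range of the whole. The size is not:

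- Lognormal readings with a CV of 0.2 to 0.4: 45.1% to 45.4%.
- Serial correlation of 0.3 to 0.6: 33% to 52%, depending on which two checks remain.
- A fasting-to-bedtime rise of 30 to 80 mg/dL with residual SD 25 to 40: about 11% (fasting and bedtime kept) to 64% (two adjacent later checks kept).

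**3. From a cut day to a difference between arms.** Let a and b be the shares of two-check days in the more-tested and less-tested arms, and r = 0.452. The relative difference is 1 − (1 − rb)/(1 − ra).

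| Share a | Share b | Range lower in less-tested arm |
|---|---|---|
| 50% | 50% | 0% |
| 40% | 50% | 1 − 0.774/0.819 = 5.5% |
| 35% | 55% | 1 − 0.751/0.842 = 10.7% |
| 30% | 60% | 1 − 0.729/0.864 = 15.7% |
| 0% | 100% | 45.2% |

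**4. False-positive rate.** Simulated trials had identical glucose in both arms and 70 residents per arm (half of the 140 in VIII.b). Stay had mean 48.9 and SD 50 days (figures from VIII.a, read as mean and SD), limited to 3 to 180 days. Within-day SD was about 35 mg/dl (assumed), the two-check days were unrelated to glucose, and the test was a two-sided Wilcoxon at 0.05. Each scenario had 200 to 1,000 runs.

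- Shares 50/40: about 20%.
- Shares 55/35: 51% to 57%.
- Shares 60/30: 87% to 90%.
- Equal shares: 4% to 8%, which is simulation noise around 5%.

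**5. Alternative measures.** With independent readings and a true SD of 40 over 49 days, the whole-study SD averages 39.9 at four checks a day and 39.9 at two. A harder case uses an assumed 60 mg/dl fasting-to-bedtime rise, fixed retained check times and shares of 60/30:

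| Measure | False positives |
|---|---|
| Daily range, all readings | 83% to 100% |
| Pooled within-day SD, all readings | 26% to 58% |
| Whole-study SD | 16% to 18% |
| Same scheduled check times in both arms | about 3% to 5% |

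The pooled within-day SD fails here because the retained times are not exchangeable with the dropped ones. It came out about 7% higher on linagliptin when fasting and bedtime were kept, and about 5% lower when two adjacent later checks were kept.

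**The case against.** Four points on the other side have force.

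- **Low stakes.** Variability is not among the outcomes listed in IV.c, the main secondary endpoints in VIII.a or the secondary endpoints in VIII.c. No hypothesis or power calculation rests on it, and the Wilcoxon test applies to it only through a general statement about continuous variables. This stands and keeps the severity low.
- **A companion measure exists.** The whole-study SD in the same sentence is much less sensitive to reading count, so a discordant result would be visible. This stands, although step 5 shows that it is not immune when glucose has a daily pattern.
- **The 45% is model-based.** It assumes independent, identically distributed normal readings, whereas the checks fall at physiologically different times. This stands, and the assumed range of about 11% to 64% belongs beside it.
- **Both arms may cut checks in nearly the same words.** Both also need pre-meal readings for correction insulin above 200 mg/dl. This stands: every share in steps 3 and 4 is assumed, and equal use gives no bias.

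A reader might infer that the plan builds in a 45% advantage for linagliptin. The documents do not support that. The 45% describes a single day that is cut, would become a between-arm difference only if one arm were always cut and the other never, and nothing in the documents states how often either arm will be cut.

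**Conclusion.** The point holds in a limited form. As written, the daily range mixes glucose variability with testing frequency. The direction is certain: fewer readings can only lower it. For independent normal readings the loss on a cut day is 45% from four checks and 33% from three, with about 11% to 64% for the former under the assumed profiles.

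Bias between arms also requires unequal use of the cut or of unscheduled checks, which the documents make plausible but do not establish. If the shares of two-check days differed by 10 to 30 percentage points, as assumed above, the range would be about 5% to 16% lower in the less-tested arm, with false positives of roughly 20% to 90%.

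It would go too far to infer that the trial's main conclusion is affected. The finding concerns one of two measures of an unlisted outcome and says nothing about the non-inferiority comparison of mean glucose. Severity is low, but the repair is cheap.

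**What to change.** In VIII.a, compute the daily range (or a within-day SD) only from one fixed set of scheduled check times, the same in both arms, on days when all of those checks are present. Exclude recheck, symptom-triggered and physician-requested values. Report readings per day by arm, and present the whole-study SD beside the range.

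Do not simply substitute a pooled within-day SD over differing check times, since step 5 shows that it remains biased when glucose has a daily pattern.

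The monitoring schedules in the IV.e arm lists and the IV.e monitoring item must be reconciled, so that the analysis can name check times that exist under the protocol.

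The cost is one or two sentences of SAP wording and a few lines of code, with no new data. Some readings and days are discarded, and the result is slightly less comparable with earlier reports of the daily range. The simulated protection assumes that cut days are unrelated to glucose. If checks are cut because a resident is stable, the complete days are a selected subset, which is a further reason to show readings per day by arm.
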